5.1 Summary of subject disposition, demographics, and baseline characteristics

5.1.1 Subject disposition

All subjects who provide informed consent will be included in disposition summaries. The number of subjects screened, screen failed, randomized, completed, and discontinued from the study, as well as reason for discontinuation, will be summarized by treatment group and overall. The number of subjects in each analysis set will also be summarized. All disposition data will listed by subject.

5.1.2 Demographics and other baseline characteristics

Descriptive summaries of the demographic and other baseline characteristics will be provided by treatment group and overall using the ITT analysis set. These tabulations will include the following variables:

- Demographics (age, age strata, sex, ethnicity, race, height, weight, and BMI)
- CNV type

- KBIT-2 Verbal, Nonverbal, and IQ Composite standard scores
- CBCL syndrome and problem standard scores and clinical range categories

All demographics and other baseline characteristics data will be listed by subject.

5.1.3 Baseline disease characteristics

Descriptive summaries of baseline disease characteristics will be provided by treatment group and overall using the ITT analysis set. These tabulations will include the following variables:

- ADHD subtype
- Age at ADHD diagnosis
- Time since ADHD diagnosis
- Age at ADHD onset
- Baseline ADHD-RS-5 total and subscale scores
- Baseline CGI-S score

All baseline disease characteristics data will be listed by subject.

5.1.4 Medical history

All medical history data will be listed by subject.

5.1.5 Prior medications and behavioral therapies

The incidence of prior medication use will be summarized by treatment group and overall and by preferred term using the ITT analysis set. Each prior medication reported more than one time will only be counted once per subject for each preferred term. All prior medication use and behavior therapy data will be listed by subject.

5.2 Protocol deviations

Major protocol deviations will be summarized by treatment group and overall using the ITT analysis set. All inclusion/exclusion criteria and protocol deviation data (including all major and minor deviations) will be listed by subject.

5.3 Primary efficacy analysis

The change from baseline in ADHD-RS-5 total score will be analyzed with mixed model repeated measures (MMRM) methods using the full analysis set. The model will include derived visit (see Section 4.7), age stratum, treatment group, and treatment-by-visit interaction as fixed factors and baseline ADHD-RS-5 total score as a covariate. Robust variance estimates for the fixed effects will be used for testing treatment differences. Within subject variability will be modeled using an unstructured (i.e., TYPE = UN) covariance pattern. In case of convergence problems, a banded Toeplitz (i.e., TYPE = TOEP(5)) structure for the covariance pattern will be used. The comparison of interest will be the difference between the AEVI-001 and placebo treatment groups at Visit 8. Model based point estimates (i.e., least square [LS] means for each treatment group and the treatment difference), 95% confidence interval for the difference, p-value, and effect size will be reported for each derived visit. Effect size will be calculated as the LS mean difference divided by an estimate of the pooled standard deviation.

Similar MMRM methods will be used to test for treatment differences in each CNTN4 CNV subgroup (see Section 4.3.8 for definition of CNTN4 CNV indicator). To control the overall type I error rate for these subgroup comparisons, a hierarchical testing procedure will be used with comparisons of the primary efficacy variable tested in the following fixed sequence:

- Full analysis set
- Full analysis set CNTN4 CNV subgroup
- Full analysis set Non-CNTN4 CNV subgroup

Supportive MMRM analyses of the primary endpoint will also be performed using the PP analysis set.

Descriptive statistics for the ADHD-RS-5 total score and change from baseline in ADHD-RS-5 total score will be presented by treatment group and derived visit. A similar descriptive statistics display will also be presented by CNTN4 CNV indicator and age stratum.

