### 14.1 Study Endpoints

### 14.1.1 Efficacy

In each part of the study, the primary outcome will be the change from baseline in the ADHD-RS-5 total score at Visit 8 (Week 6), where baseline is defined as the last ADHD RS-5 total score assessment prior to the first dose of investigational product (usually at Visit 2/Day 0).

The primary efficacy analysis will be conducted using the Full Analysis Set for the change from baseline for the ADHD-RS-5 total score, including all assessments from Visit 3 (Week 1) up to Visit 8 (Week 6), using the linear mixed models repeated measures (MMRM) methods with treatment group, visit, and baseline ADHD-RS-5 total score as a covariate, and interaction of the baseline ADHD-RS-5 total score with the visit included in the model. Missing data will not be imputed.

The primary contrast of interest will be the comparison of the AEVI-001 and placebo groups at Visit 8 (Week 6).

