### 14.3 Statistical Analyses

This section presents a summary of the planned statistical analyses. Additional details regarding data handling, analytical methods, and presentation of results will be found in the Statistical Analysis Plan (SAP) for this study. The SAP will be finalized prior to database lock.

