2.2 Study design

This is a 2-part, 6-week, double-blind, dose-optimization, parallel-group study in children and adolescents (ages 6-17 years) with ADHD with and without CNVs in specific genes implicated in glutamatergic signaling and neuronal connectivity (see Figure 1 for the study design of both parts). Only subjects who had genetic testing performed during another Aevi study (i.e., MDGN-NFC1-ADHD-001, MDGN-NFC1-ADHD-101, or AEVI-001-ADHD-002) and who consented to future research were considered for participation in this study. Part A will include subjects determined to have one of 8 specific gene mutation(s) implicated in glutamatergic signaling and neuronal connectivity. Part B will be conducted and will assess subjects who do not have CNVs in any of the 272 specific gene mutation(s) implicated in glutamatergic signaling and neuronal connectivity. The list of excluded mutations includes the 8 gene mutations studied in Part A and an additional 264 mutations identified in an antecedent study. Once subjects are confirmed as eligible for each part of the study, they will be randomized to one of two treatment groups (AEVI-001 or placebo) in a 1:1 ratio. The randomization will be stratified by age (6 to 12, 13 to 17 years old) and part (A, B) with each part of the study analyzed separately.

During both parts of the study, randomized subjects will receive investigational product (IP) at the Baseline Visit (Visit 2; Day 0) and will begin taking IP at a dose of 100 mg twice daily on Day 1, once in the morning upon awakening (between 7:00 AM to 9:00 AM) and once in the mid-afternoon (between 3:00 PM to 5:00 PM). Dosing will be optimized weekly (± 2 days) to 100 mg, 200 mg, or 400 mg twice daily, as appropriate, over the first 4 weeks of treatment (Dose-optimization Period), based on clinical response and tolerability. If the subject tolerates a dose well, the dose will be maintained for an additional 2 weeks (Dose Maintenance Period). Visits during the Dose-optimization and Dose Maintenance Periods are to be conducted every 7 days (± 2 days). Visits conducted after randomization should be scheduled relative to the Baseline Visit (Visit 2). The primary assessments of safety and efficacy will be performed weekly during the 6-week treatment period. A follow-up telephone call will be performed 7 days (± 2 days) after the last dose of IP. The complete Schedule of Events is included in Appendix A.

[figure not shown]

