2.3 Determination of sample size

For Part A of the study, 42 unique subjects are planned to be randomized to yield approximately 34 subjects who provide post-baseline efficacy data on the primary endpoint. Assuming an effect size of 1.0, this number will yield approximately 80% power to detect a significant difference in mean change from baseline for the ADHD-RS-5 total score at Visit 8 (Week 6) between the treatment groups, based on a 2-tailed test with $\alpha = 0.05$ and 1:1 randomization. In Part A of the study, an interim analysis will be performed when approximately 75% of randomized subjects have completed the study. The sample size could be increased to 64 randomized subjects.

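### SAP 5.3 tests the Visit 8 contrast with robust variances in about 34–42 subjects, and in smaller CNTN4 subgroups, without naming a small-sample correction or degrees of freedom

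*SAP*

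**What the plan says.** Protocol 14.1.1 describes the primary analysis as "using the linear mixed models repeated measures (MMRM) methods with treatment group, visit, and baseline ADHD-RS-5 total score as a covariate" and gives no variance method. Protocol 14.3 passes the matter on: "Additional details regarding data handling, analytical methods, and presentation of results will be found in the Statistical Analysis Plan (SAP) for this study".

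SAP 5.3 specifies visit, age stratum, treatment and treatment-by-visit as fixed factors, the baseline score as a covariate, and an unstructured covariance with TOEP(5) as fallback. On inference it says only: "Robust variance estimates for the fixed effects will be used for testing treatment differences". It does not state the form of the estimator, a small-sample correction, degrees of freedom or a reference distribution. SAP section 5 names the software, and SAP 6.1 lists no changes from the protocol.

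SAP 5.3 then adds: "Similar MMRM methods will be used to test for treatment differences in each CNTN4 CNV subgroup". The full set, the CNTN4 subgroup and the non-CNTN4 subgroup are tested in that order, with this purpose: "To control the overall type I error rate for these subgroup comparisons, a hierarchical testing procedure will be used".

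On size, SAP 2.3 says "42 unique subjects are planned to be randomized to yield approximately 34 subjects who provide post-baseline efficacy data", and "The sample size could be increased to 64 randomized subjects". No CNTN4 subgroup size is given. SAP 2.2 stratifies randomization by age group and study part, not by CNTN4 status. The Protocol Synopsis sets all tests two-sided at 0.05.

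**The concern.** The ordinary sandwich estimator builds the variance from squared residuals. Fitting the model shrinks those residuals, so with few subjects the variance is too small on average and the test rejects too often. Part A has few subjects for a model with 14 fixed effects and 21 covariance parameters, and the subgroup analyses have fewer still.

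Two things are at stake. The primary test may not hold its stated 5% level. The CNTN4 step, second in the sequence, would be distorted most, because a fixed sequence protects the error rate only if each test in it has its nominal size. Protocol 6.1 names CNTN4 as the most frequent variant in the earlier study and makes replication of that study's gene finding the focus of this one.

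**Working it through.** **1. The plan's own figure.** With 17 per arm, effect size 1.0 and two-sided 0.05, the noncentrality is √(17/2) = 2.915 on 32 degrees of freedom (critical value 2.037). Power is 80.7%, so the stated 80% is reproduced. It rests on an ordinary t-test and is not in dispute.

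**2. Model size.** Fixed effects: 1 intercept + 5 visit + 1 age + 1 treatment + 5 interaction + 1 baseline = 14. Unstructured covariance for 6 visits: 6 × 7 / 2 = 21.

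**3. Subgroup size.** The two subgroups add up to the full set, so with 42 subjects the smaller has at most 42 / 2 = 21.

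**4. Hand approximation.** Four between-subject parameters bear on the Visit 8 contrast: two arm means, age stratum and baseline. Squared residuals are therefore too small by roughly 1 − 4/n, and the standard error by k = √(1 − 4/n). The actual error is then about
- P(|T| > k × t(0.975; n−4)) with a t reference,
- P(|T| > 1.96 k) with a normal reference,

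where T has n−4 degrees of freedom. Example for n = 34: k = √(30/34) = 0.939. With t, the cut-off is 0.939 × 2.042 = 1.918, giving 6.46%. With the normal, it is 0.939 × 1.96 = 1.841, giving 7.55%.

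**5. Simulation under no treatment effect.** Both simulations used the SAP fixed effects, six visits, a REML unstructured fit and the uncorrected sandwich.
- Simulation 1: SD rising from 7 to 11, exchangeable correlation 0.6. Subgroups were drawn at random, so their arms could be unequal. Dropout was completely at random to 81% remaining at Week 6 for n = 64, 42, 26, 21 and 16; data were complete at 34, 17 and 13. Monte Carlo standard error 0.25–0.45 points.
- Simulation 2: AR(1) correlation 0.7. Dropout of 19% at n = 64 and 42; otherwise complete. Monte Carlo standard error about 0.4 points.

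Two-sided error at Visit 8 in %, t(n−4) / normal:

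| n | k | Hand | Simulation 1 | Simulation 2 |
|---|---|---|---|---|
| 64 | 0.968 | 5.75 / 6.25 | 5.5–6.2 / 6.0–6.7 | 5.7 / 6.2 |
| 42 | 0.951 | 6.17 / 7.00 | 5.8 / 6.7 | 6.4 / 7.1 |
| 34 | 0.939 | 6.46 / 7.55 | 6.4 / 7.4 | 5.9 / 6.8 |
| 26 | 0.920 | 6.96 / 8.51 | 7.3 / 8.9 | – |
| 24 | 0.913 | 7.14 / 8.87 | – | 6.4 / 8.4 |
| 21 | 0.900 | 7.48 / 9.58 | 7.9 / 9.8 | – |
| 18 | 0.882 | 7.94 / 10.59 | – | 8.6 / 10.6 |
| 17 | 0.874 | 8.14 / 11.03 | 8.1 / 10.9 | – |
| 16 | 0.866 | 8.36 / 11.54 | 9.3 / 12.7 | – |
| 14 | 0.845 | 8.91 / 12.86 | – | 9.0 / 12.7 |
| 13 | 0.832 | 9.25 / 13.74 | 9.5 / 13.9 | – |

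Sensitivity:
- Four covariances in Simulation 1 gave 5.3–6.5 / 6.1–7.5 at n = 34 and 42, and 7.8–8.9 / 9.8–11.6 at n = 21.
- A further 19% dropout from n = 34 in Simulation 2 gave 6.8 / 8.0.
- Balanced arms at n = 17 lowered the t figure to about 6.5–7.

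**6. With a correction and t(n−4).** Mancl-DeRouen gave 3.6–5.2% in Simulation 1 and 3.8–4.5% in Simulation 2. Model-based REML variance gave 4.4–6.3% in Simulation 1. A Kauermann-Carroll-type correction in Simulation 2 gave 4.8–5.7% in the full set at 34–42, but 6.4–6.5% at n = 14–18.

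**7. Power at effect size 1.0** (uncorrected / Mancl-DeRouen / model-based): n = 34, 82.3 / 78.5 / 80.3%; n = 42, 85.5 / 81.7 / 83.9%. The uncorrected figure is flattered by an oversized test.

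**8. Fixed sequence.** If there is no effect anywhere, nothing can be claimed unless the full-set test rejects. The familywise excess is therefore that of the first step: 5.3–6.5% less 5%, or 0.3–1.5 points with t.

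**The case against.** **The SAP never says the variance is uncorrected.** True. A program that applies a correction and suitable degrees of freedom would remove most of the problem. A reader might infer that the primary test is wrong as planned; the documents do not support that. They leave the choice open, and the commonest form has a known bias.

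**The effect on the primary test is small, and this is Phase 2.** This stands. The excess is about 0.5–1.5 points with t, and less if enrolment reaches 64.

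**Not every subgroup is badly affected.** This also stands. A reader might infer that both subgroup tests are clearly oversized. No subgroup size is given, the larger one may be well above 21, and after enlargement both could be about 32. At 24–26 the error is only about 6.5–7.5% with t.

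**The 95% interval is not tied to the robust variance.** SAP 5.3 names it for testing and lists the interval separately. Using one variance for both is the natural reading, but it is not stated.

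**The fixed sequence does not obviously fail.** A reader might infer that false CNTN4 claims would exceed 5%. In four configurations with an overall effect of 1.0 lying wholly in non-CNTN4 subjects, the rate was 4.2–6.9%, above 5% in only two. Those settings need a non-CNTN4 effect of 1.0 / (21/42) = 2.0 SD or 1.0 / (28/42) = 1.5 SD. With a non-CNTN4 effect of 1.0 SD and complete data, the rate was about 2.8% (CNTN4 21 of 42) and 4.1% (14 of 42). A failure of familywise control is therefore not shown, although the second test remains oversized once it is reached.

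**The simulations do not reproduce the TOEP(5) fallback.** Non-converged fits (1–2% at n = 13–16) were excluded, and the code was not SAS, so nothing can be said about how often the fallback would be used. A full Toeplitz working structure, which is not the banded one, still gave 6.5% at n = 24 and 8.1% at n = 18 with t.

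**Mancl-DeRouen is not the only sound remedy.** Agreed: it is slightly conservative. The need is to prespecify one adequate method.

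**Conclusion.** The point holds as a conditional one. SAP 5.3 prescribes robust variances for the full-set test and both CNTN4 tests without a small-sample correction or degrees of freedom, and no other passage supplies them. In the ordinary uncorrected form:

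- **Full set** (34–42, or up to 64): error about 5.5–6.5% with t(n−4), up to about 7–8% with a normal reference. Standard errors are about 3–6% too small.
- **Subgroup of about 13–21:** about 8–10% with t, 10–14% with normal.
- **Subgroup of about 24–26:** about 6.5–7.5% with t.

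Interval coverage falls by the same amounts if the interval uses the same variance.

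The figures rest on assumed SDs, correlations, dropout pattern and subgroup sizes, and on n−4 or normal as the reference. The direction does not depend on those choices: two simulations with different covariances and the hand approximation agree. The bound of 21 for the smaller subgroup without enlargement is arithmetic. The use of a robust variance is not itself a fault. The point should be fixed before unblinding, because the possible corrections give materially different p-values in small subgroups.

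**What to change.** Add one sentence to SAP 5.3 that fixes a single method for the full analysis set and both CNTN4 subgroups. Either would do:

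- *Treatment comparisons and their confidence intervals will use robust variance estimates with the Mancl-DeRouen small-sample correction and n−4 between-subject degrees of freedom, where n is the number of subjects in that analysis.*
- *Treatment comparisons and their confidence intervals will use model-based REML variances with Kenward-Roger degrees of freedom under the unstructured covariance; if the TOEP(5) structure is used, the Mancl-DeRouen corrected robust variance with n−4 degrees of freedom will be used instead.*

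The uncorrected sandwich can stay as a sensitivity analysis. SAP 5.4 refers back to 5.3 for its MMRM analyses, so the same sentence would settle those too.

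The cost is one SAP sentence and one programming option. At effect size 1.0 and n = 34, power goes from 82.3% to 78.5% with Mancl-DeRouen (about 4 points) or to 80.3% with model-based variance (2 points); the latter was computed with n−4 rather than Kenward-Roger degrees of freedom. Both remain close to the planned 80%. Relative to the uncorrected form, Mancl-DeRouen standard errors are about 7–10% larger at 34–42, 5% at 64, 13% at 26, 16–20% at 21 and 23–26% at 13–16, and the test becomes slightly conservative.

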4.7 Efficacy variables

For each efficacy assessment, study day will be calculated as: the date of assessment – the date of first dose of study drug + 1. As deviations are expected in the number of days from the date of first dose (i.e., study day 1) to the study day that planned assessments actually occur, visit windows will be used to derive visit numbers for use in efficacy analyses. Efficacy variable visit windows and their associated derived visit numbers and labels are defined in Table 2.

Derived visit number	Derived visit label	Visit window (days)
1	Visit 1	≤-1
2	Visit 2 (Week 0)	0
3	Visit 3 (Week 1)	1 to 11
4	Visit 4 (Week 2)	12 to 18
5	Visit 5 (Week 3)	19 to 25
6	Visit 6 (Week 4)	26 to 32
7	Visit 7 (Week 5)	33 to 39
8	Visit 8 (Week 6)	40 to 50

 Table 2: Visit windows for efficacy variables

For all efficacy variables, baseline will be defined as the last assessment prior to the first dose of IP. Change from baseline values will be calculated as the assessment value minus the baseline value. For the derivation of any total or subscale score, if at least 80% of the items needed to calculate a score have valid responses, then that score will be computed as the sum of all non-missing items divided by the percentage of non-missing items in that scale or subscale. If fewer than 80% of the items have valid responses, then that score will be considered as missing.

For some efficacy variables, the last observation carried forward (LOCF) method of imputation will be used to calculate additional LOCF efficacy variables. For LOCF variables, a derived visit number of 99 and a visit label of "LOCF" will be assigned.

4.7.1 Attention Deficit Hyperactivity Disorder Rating Scale Version 5

The Attention Deficit Hyperactivity Disorder Rating Scale Version 5 (ADHD-RS-5; DuPaul et al., 2016) is a parent reported/clinician-rated scale designed to reflect the symptomatology of ADHD based on the Diagnostic and Statistical Manual of Mental Disorders, Fifth Edition (DSM-5) criteria. The ADHD-RS-5 is comprised of 18 frequency items and 12 impairment items. Each frequency item will be scored on a scale from 0 = "Never or rarely" to 3 = "Very often". Each impairment item will be scored on a scale from 0 = "No Problem" to 3 = "Severe Problem". Each ADHD-RS-5 item score will be recorded in the eCRF.

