5.4 Secondary efficacy analyses

Logistic regression methods will be used for the analysis of the LOCF ADHD-RS-5 response indicator using the full analysis set. The logistic regression model will include terms for age stratum, treatment group, and baseline ADHD-RS-5 total score. The comparison of interest will be the difference between the AEVI-001 and placebo treatment groups at end-of-treatment. Model based point estimates (i.e., odds ratios), 95% confidence intervals, and p-value will be reported.

Similar logistic regression models will be used for the LOCF CGI-I remission, LOCF combined ADHD-RS-5/CGI-I response, and LOCF combined ADHD-RS-5/CGI-I remission indicators using the full analysis set. For the CGI-I response/remission analyses, baseline CGI-S score will be included in the model. For the combined response/remission analyses, baseline ADHD-RS-5 total and CGI-S scores will be included in the model.

MMRM methods similar to those described in Section 5.3 will be used for the analysis of the following change from baseline values: ADHD-RS-5 inattention subscale, ADHD-RS-5 hyperactivity–impulsivity subscale, and CGI-S, Conners 3-P(S) inattention subscale, Conners 3-P(S) hyperactivity–impulsivity subscale, Conners 3-P(S) learning problems subscale, Conners 3-P(S) executive function subscale, Conners 3-P(S) aggression subscale, and Conners 3-P(S) peer relations subscale. For each model, the baseline score of the respective subscale used in the model will be used as a covariate. For the models including Conners 3-P(S) subscale scores, a heterogeneous first order autoregressive (i.e., TYPE = ARH(1)) covariance structure will be used in cases of convergence problems. As with the primary efficacy analysis, the comparison of interest for each model will be the difference between the AEVI-001 and placebo treatment groups at Week 6. Model based point estimates (i.e., LS means for each treatment group and the treatment difference), 95% confidence interval for the difference, p-value, and effect size will be reported for each derived visit.

Subgroup analyses by ADHD subtype (see Section 4.4.1) will be performed for select secondary efficacy variables. No multiplicity correction to the reported p-values will be made for any secondary efficacy analysis. Supportive analyses of secondary efficacy endpoints may be performed using the PP analysis set.

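### The only fallback covariance for the primary MMRM, TOEP(5), sets the Week 1 to Week 6 covariance to zero and can bias the Week 6 difference if it is used and dropout depends on earlier scores

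*SAP*

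**What the plan says.** Protocol 14.1.1 defines the primary model as a repeated-measures analysis of change in ADHD-RS-5 total score, "including all assessments from Visit 3 (Week 1) up to Visit 8 (Week 6"), and states "Missing data will not be imputed". SAP 4.7 says "visit windows will be used to derive visit numbers for use in efficacy analyses"; its Table 2 gives six post-baseline visits, Visit 3 (Week 1) to Visit 8 (Week 6).

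On the covariance, SAP 5.3 says "Within subject variability will be modeled using an unstructured (i.e., TYPE = UN) covariance pattern" and then "In case of convergence problems, a banded Toeplitz (i.e., TYPE = TOEP(5)) structure for the covariance pattern will be used". No further fallback follows. On inference it says "Robust variance estimates for the fixed effects will be used for testing treatment differences" and "The comparison of interest will be the difference between the AEVI-001 and placebo treatment groups at Visit 8". The CNTN4 and non-CNTN4 subgroups are tested with similar models.

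SAP 5.4 extends the approach: "MMRM methods similar to those described in Section 5.3 will be used" for the two ADHD-RS-5 subscales, CGI-S and six Conners subscales. The Conners models have their own fallback, ARH(1).

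**The concern.** A full Toeplitz structure for six visits has six bands. With five, one covariance is set to zero by the model rather than estimated: that between the first post-baseline visit and the visit of the primary contrast. Children who score high or low relative to their arm at Week 1 can be expected to do so to some degree at Week 6, even after adjustment for baseline. The SAP does not say that it intends otherwise.

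The covariance matters because missing scores are not imputed. Under missing at random, the likelihood uses it to carry a leaver's observed scores forward to Week 6. For a subject last seen at Week 1, TOEP(5) carries nothing forward. A sandwich variance protects the standard error against a wrong covariance, but it does not move a biased estimate back. At stake is the primary Part A estimate, in the event that the first-choice model does not converge.

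**Working it through.** **The plan's own figure.** No figure in the plan concerns the covariance. The nearest is power: 17 per arm, effect size 1.0, two-sided 0.05. A noncentral t with 32 df and noncentrality √(17/2) = 2.92 gives 80.7%, which agrees with the stated 80%. Nothing below disputes it.

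**Step 1: parameters for six visits.**
- Unstructured: 6 × 7 / 2 = 21
- TOEPH: 6 variances + 5 correlations = 11
- TOEP: 6
- TOEP(5): 5

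**Step 2: what is set to zero.** Lag k has 6 − k visit pairs, so lag 5 has exactly one: Week 1 with Week 6.

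**Step 3: can the other lags stay as they are?** Take a common correlation ρ and set only lag 5 to zero. The matrix stays positive definite while 1 + 3ρ − 8ρ² > 0, that is, for ρ < (3 + √41)/16 = 0.588. The smallest eigenvalue is 0.149 at ρ = 0.5, −0.021 at 0.6 and −0.191 at 0.7. Above the threshold the fit must shrink the other lags to be admissible. Even below it they may shift: AR(1) with 0.8 stays positive definite (smallest eigenvalue 0.019), yet its lags are pulled down in Step 4.

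**Step 4: fitted correlations in large samples.**

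| True lags 1-5 | Fitted by TOEP(5) |
|---|---|
| 0.80, 0.74, 0.68, 0.62, 0.56 | 0.74, 0.60, 0.43, 0.23, 0 |
| 0.80, 0.72, 0.65, 0.58, 0.52 | 0.75, 0.59, 0.41, 0.22, 0 |
| 0.60 at all lags | 0.47, 0.43, 0.38, 0.30, 0 |
| AR(1), 0.8 | 0.77, 0.56, 0.36, 0.18, 0 |

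**Step 5: effect on the Week 6 difference.** SD, correlations and dropout mechanism are assumptions. The documents give only an allowance of (42 − 34)/42 = 19% for subjects without post-baseline data, and nothing on missingness at Week 6. The first set of fits used 40,000 per arm, SD 10, true difference −10 (the plan's effect size of 1.0), monotone missing-at-random dropout and arm-by-visit means. Baseline and age stratum were omitted. Cells show TOEP(5) / full TOEP.

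| Dropout | Common 0.6 | AR(1) 0.8 | 0.80 to 0.52 |
|---|---|---|---|
| Same lack-of-efficacy rule in both arms (12-21%) | −9.74 / −10.02 | −9.87 / −10.05 | −9.67 / −9.94 |
| Opposite direction by arm (23-26%) | −8.16 / −9.98 | −8.88 / −9.99 | −8.23 / −10.04 |
| Opposite direction, all right after Week 1 (22-23%) | −6.65 / −10.09 | −7.99 / −9.91 | −6.98 / −10.02 |

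With complete data the shift was 0.00. Full TOEP stayed within 0.03 points of generalised least squares under the true covariance. At 42 subjects only 10 to 14 replicates per scenario were run, so these are indicative: mean TOEP(5) minus TOEP was 0.03 (SE 0.24) under one rule, and 1.19 (SE 0.23) and 1.80 (SE 0.31) with opposite directions.

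A second set used SD 10, true difference 8, 15-29% dropout and lag-5 correlations of 0.17-0.56. The last column divides by 8.

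| Dropout | Shift toward zero, points | Share of 8 |
|---|---|---|
| Unrelated to outcome | about 0 | about 0% |
| Same rule in both arms | 0.04-0.14 | 0.5-1.8% |
| Only placebo dropout follows outcome | about 0.2-0.7 | 2.5-9% |
| Opposite direction by arm | about 0.4-1.5 | 5-19% |

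For scale, the standard error with 17 per arm is 10 × √(2/17) = 3.43 points.

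**Step 6: is full TOEP enough?** Those simulated truths had equal variances at all visits, which favours TOEP. With SD rising from 7 to 12 across visits, opposite-direction dropout and a true −8, full TOEP gave −7.09 and TOEP(5) gave −6.43. TOEP therefore left 0.91 of the 1.57 points of bias.

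**The case against.** **The unstructured model may simply converge.** In 151 simulated trials of 34 subjects with about 18% dropout, an EM fit of the unstructured model converged every time. That was not SAS PROC MIXED, and it omitted baseline and age stratum. Also, the CNTN4 subgroups are smaller than the full set, and the documents do not give their sizes. How often the fallback would be used is therefore unknown, and the concern remains conditional.

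**A reader might infer that the primary estimate is biased as planned.** The documents do not support that. Bias needs both a failed unstructured fit and outcome-related dropout. With one rule in both arms it is a few percent of a standard error (0.14/3.43 = 4%).

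**A reader might take the largest shifts as expected.** They need dropout running in opposite directions by arm, which nothing in the documents predicts. Protocol 9.7 keeps in the study, in both arms, subjects who tolerate the highest dose without an acceptable response. However, Protocol 8.7 lists both adverse events and lack of efficacy as reasons to leave, and the mix may differ by arm. The intermediate case is therefore plausible.

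**A reader might argue that changes from one shared baseline cannot be uncorrelated.** Baseline score is a covariate, so that source is largely removed. The case for a non-zero lag 5 rests on other persistent differences between children. Decay could also be faster, since Week 1 is on the starting dose and Week 6 on an optimised one. With AR(1) 0.6, true −8 and opposite-direction dropout, the gap was only 0.14 (−7.82 against −7.96).

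**Banding is named and prespecified, and no passages conflict.** This stands: it is not an inconsistency. But no reason is given for a zero at this pair.

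**Conclusion.** The structural point is exact: with six visits, TOEP(5) fixes the Week 1 to Week 6 covariance at zero and distorts the remaining correlations. The consequence is conditional. If the fallback is used and dropout depends on earlier scores, the Week 6 difference can be biased. In the scenarios with a true effect the bias ran toward zero, but the direction depends on the mechanism. The second set of assumptions in the working gives anything from nil to about 1.5 points. The first set gave larger shifts, up to 3.4 points (−6.65 against −10.09) in its stress case of early, opposite-direction dropout. These sizes illustrate the risk and do not predict this trial's bias.

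The reach is the primary model, the CNTN4 subgroup models and, in SAP 5.4, the two ADHD-RS-5 subscales and CGI-S: three of the nine outcomes listed there. The Conners models are not affected. This is a cheap improvement to a contingency analysis, not an error in the planned first-choice model.

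**What to change.** In SAP 5.3, replace TYPE=TOEP(5) with a prespecified sequence that keeps every lag: TYPE=TOEPH first, then TYPE=TOEP if TOEPH does not converge. Fix it before unblinding, so that the structure is not chosen with results in view. State that the same sequence applies to the CNTN4 subgroup models and, in 5.4, to the ADHD-RS-5 subscales and CGI-S. Leave the Conners fallback as it is.

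The cost is one more covariance parameter for TOEP (6 instead of 5). TOEPH has 11 and may itself fail to converge after the unstructured model has failed, hence the second step. TOEP can leave some bias if variances differ by visit, which is the reason for trying TOEPH first.
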